4.4.1 Palliative Medicine and Supportive Care

In the event patients develop adverse events requiring palliative care, investigator will refer patient to primary care physician (PCP).

4.3.2 Supportive Management for Diarrhea in Patients Receiving Abemaciclib

Patients should receive instructions on the management of diarrhea. In the event of diarrhea, supportive measures should be initiated as early as possible. These include the following:

- At the first sign of loose stools, the patient should initiate anti-diarrheal therapy (e.g., loperamide) and notify the investigator for further instructions and appropriate follow-up.
- Patients should also be encouraged to drink fluids (e.g., 8 to 10 glasses of clear liquids per day).
- Site personnel should assess response within 24 hours.
- If diarrhea does not resolve with anti-diarrheal therapy within 24 hours to at least Grade 1 (per CTCAE v 5.0), study abemaciclib treatment should be suspended until diarrhea is resolved to at least Grade 1.
- When abemaciclib treatment recommences, dosing should be adjusted as outlined in Section 4.2.1. In severe cases of diarrhea, the measuring of

CONFIDENTIAL

This material is the property of the [UC Irvine Chao Family Comprehensive Cancer Center](#). Do not disclose or use except as authorized in writing by the study sponsor.

neutrophil counts and body temperature and proactive management of diarrhea with antidiarrheal agents should be considered.

If diarrhea is severe (requiring intravenous rehydration) and/or associated with fever or severe neutropenia, broad-spectrum antibiotics such as fluoroquinolones should be considered. Patients with severe diarrhea or any diarrhea associated with severe nausea or vomiting should be carefully monitored and given intravenous fluid and electrolyte replacement as clinically indicated.

4.5 Duration of Therapy

In the absence of treatment delays due to adverse events, treatment may continue until:

- Maximum response (per investigator discretion based on clinical and/or imaging assessments) is obtained OR
- Disease progression as defined radiographic progression by RECIST v1.1 criteria OR death OR symptomatic progression as clinically determined by the treating physician
- Inter-current illness that prevents further administration of treatment
- Unacceptable adverse event(s)
- Patient decides to withdraw from the study, **OR**
- General or specific changes in the patient's condition render the patient unacceptable for further treatment in the judgment of the investigator

4.6 Duration of Follow Up

Patients will be followed every 6 months after surgery for ctDNA blood collection. The follow up phase will continue until study completion at 5 years or until death, whichever occurs first.

4.7 Removal of Patients from Protocol Therapy

Patients will be removed from therapy when any of the criteria listed in [Section 5.5](#) apply. Notify UCI CFCCC via secure email ([contact] and [contact]), and document the reason for study removal and the date the patient was removed in OnCore. The patient should be followed-up per protocol.

4.8 Patient Replacement

Patients will not be replaced

5.0 STUDY PROCEDURES

5.1 Screening/Baseline Procedures

Assessments performed exclusively to determine eligibility for this study will be done only after obtaining informed consent. Assessments performed for clinical indications (not exclusively to determine study eligibility) may be used for baseline values even if the studies were done before informed consent was obtained as long as these assessments are completed within 28 days prior to registration.

All screening procedures must be performed within 28 days prior to registration unless otherwise stated. The screening procedures include:

CONFIDENTIAL

This material is the property of the [UC Irvine Chao Family Comprehensive Cancer Center](#). Do not disclose or use except as authorized in writing by the study sponsor.

5.1.1 Informed Consent

5.1.2 Screening Confirmation

Patient information should be entered into Oncore within 1 business day of consent. Site is responsible for assigning subject ID. Subject IDs should follow a format with the unique site code followed by sequential patient ID. For example, Site Code-Sequential Number (i.e. for first patient the subject ID will be 01-01). Refer to Oncore SOP for Oncore data entry instructions.

5.1.3 Medical history

Complete medical and surgical history

5.1.4 Demographics

Age, gender, race, ethnicity

5.1.5 Review subject eligibility criteria

5.1.6 Review previous and concomitant medications

5.1.7 Physical exam

5.1.8 Vital signs, height and weight

Temperature, pulse, respirations, blood pressure, weight and height (height only at screening)

5.1.9 ECOG Performance status

Refer to Appendix A

5.1.10 Hematology

Complete blood count (CBC) with differential

5.1.11 Blood draw for correlative studies

Blood collection for ctDNA.

5.1.12 Serum chemistries

Comprehensive metabolic panel (CMP) to include: albumin, alkaline phosphatase, ALT, AST, BUN, creatinine, electrolytes (sodium, potassium, calcium, chloride, bicarbonate), glucose, and total bilirubin.

5.1.13 Tumor assessment

To be performed with computed tomography (CT) of the chest (preferred with IV contrast) and abdomen/pelvis (preferred with IV and oral contrast) to rule out metastasis. CT abdomen/pelvis may be replaced with MRI Abdomen/pelvis (preferred with IV contrast) per clinical judgement of the treating physician. An MRI of the breast will also be required for RECIST 1.1 baseline assessment. Additional imaging is indicated at baseline if there is clinical suspicion for other organ involvement (i.e. MRI or CT brain and bone scan). Imaging is to be performed at baseline within 28 days of starting treatment

CONFIDENTIAL

This material is the property of the [UC Irvine Chao Family Comprehensive Cancer Center](#). Do not disclose or use except as authorized in writing by the study sponsor.

5.2 Registration Procedures

The below items must be reviewed and confirmation of eligibility must be completed by the PI and CRM prior to registration:

- Signed Informed consent
- Physical exam and complete medical and surgical history
- All screening labs
- Signed eligibility criteria

Items must be reviewed by the PI and CRM at least 3 business days before planned treatment start date.

5.3 Procedures During Treatment

5.3.1 Prior to Each Treatment Cycle

- Physical exam, vital signs
- Hematology
- Serum chemistries
- Adverse events
- Study drug accountability
- Review previous and current concomitant medications

Site must maintain an accurate and timely record of dispensing of study drug to subject, and receipt of all study drug and pill diaries.

5.3.2 Within 30 days after treatment termination

- Physical exam, vital signs
- Hematology
- Serum chemistries
- Adverse Events
- Review previous and current concomitant medications

5.2.3 Tumor Assessments

MRI breast to be completed every 12 weeks (+/- 7 days) during treatment phase

5.4 Follow-up Procedures

Patients will be followed every 6 (+/- 14 days) months after surgery until patient comes off study due to study completion at 5 years, death, or withdrawal, whichever comes first

- Blood collection for ctDNA

5.5 Time and Events Table

If baseline evaluations are conducted within 1 week prior to administration of protocol therapy, those assessments do not need to be repeated. Scans must be done \leq 4 weeks prior to the start of therapy. In the event that the patient's condition is deteriorating, laboratory evaluations should be repeated within 48 hours prior to initiation of the next cycle of therapy.

	Baseline/Screening	Treatment Phase		Post-discontinuation		
	-28 to -1 days	Cycle 1	Subsequent cycles	End of Treatment	Surgery	Follow-up

CONFIDENTIAL

This material is the property of the [UC Irvine Chao Family Comprehensive Cancer Center](#). Do not disclose or use except as authorized in writing by the study sponsor.

		D1 (-3d)	D15 (±3d)	D1 (-3d)	Within 30 days of last dose prior to surgery		Every 6 months (±14d)
Assessment							
Informed Consent	X						
History and PE	X	X		X	X		
Vital Signs	X	X	X	X	X		
Baseline medical and oncology history	X						
Concomitant Medications	X	X		X	X		
ECOG Performance Status	X	X		X	X		X
Adverse Events		X		X	X		
Tumor Measurements	X						
CT CAP or CT chest/MRI Abd/Pelvis ¹	X						
MRI Breast	X			X Every 12 weeks (±7d) after first dose until maximum response or progression, whichever occurs first			
CBC w/diff	X	X	X	X	X		
CMP	X	X	X	X	X		
Postmenopausal Confirmation	X						
ctDNA (correlative study)	X			X ²			X
Biopsy ³					X		
Tissue Submission	X				X	X	
Administer Abemaciclib		X	X	X			
Administer Fulvestrant		X	X	X			
Study Drug Accountability				X	X		

¹ CT Chest, abdomen and pelvis with contrast or CT chest/MRI Abdomen, Pelvis is required at screening to rule out metastasis

² Every 3 months during treatment

CONFIDENTIAL

This material is the property of the [UC Irvine Chao Family Comprehensive Cancer Center](#). Do not disclose or use except as authorized in writing by the study sponsor.

³ A fresh biopsy at time of progression is mandatory if clinically feasible.

5.6 Removal of Subjects from Study

Patients can be taken off the study treatment and/or study at any time at their own request, or they may be withdrawn at the discretion of the investigator for safety, behavioral or administrative reasons. The reason(s) for discontinuation will be documented and may include:

- 5.5.1 Patient voluntarily withdraws from treatment (follow-up permitted);
- 5.5.2 Patient withdraws consent (termination of treatment and follow-up);
- 5.5.3 Patient is unable to comply with protocol requirements;
- 5.5.4 Patient demonstrates disease progression (unless continued treatment with study drug is deemed appropriate at the discretion of the investigator);
- 5.5.5 Patient experiences toxicity that makes continuation in the protocol unsafe;
- 5.5.6 Treating physician judges continuation on the study would not be in the patient's best interest;
- 5.5.7 Development of second malignancy (except for basal cell carcinoma or squamous cell carcinoma of the skin) that requires treatment, which would interfere with this study;
- 5.5.8 Lost to follow-up. If a research subject cannot be located to document survival after 3 attempts including 1 mailed certified letter, the subject may be considered "lost to follow-up." All attempts to contact the subject during the two years must be documented and approved by the Data Monitoring Committee.

6.0 Measurement of Effect

6.1 Pathologic Complete Response (pCR)

No histologic evidence of microscopic invasive tumor at the primary tumor site in the surgical specimen (ypT0 or ypTis).

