2.4 Endpoints

The primary endpoint is pathological complete response (pCR) as defined by no evidence of tumor cells in the final surgical specimen
The secondary endpoints are ORR per RECIST 1.1 criteria, recurrence disease-free and incidence of AEs

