10.0 STATISTICAL CONSIDERATIONS

Pathological response (pCR) is a tool to measure the efficacy of Neo-Adjuvant therapy. A complete pCR is defined as the absence of invasive cancer in the tumor and/or the axillary lymph node in the surgical pathology specimen after undergoing Neo-Adjuvant therapy. Chemotherapy can shrink HR- positive tumors and facilitate better surgical options, but is less likely to achieve a pathologic complete response (pCR) in HR-positive cancers, especially luminal A cancers, than for more proliferative histologies. Multiple metaanalysis have shown that pCR has prognostic implications even in patients with HR+ breast cancer. However, a limitation of using pCR to predict outcomes in patients with ER+ disease is that only 2 to 10 percent of patients with ER + disease achieve a pCR with NACT. In the post-menopausal setting, Aromatase Inhibitors are recommended over Tamoxifen as Neoadjuvant endocrine therapy based on clinical trials and meta-analysis. AIs resulted in higher clinical response rate (OR 1.69, 95% CI 1.36-2.10), radiologic response rate (OR 1.49, 95% CI 1.18-1.89), and BCS rate (OR 1.62, 95% CI 1.24-2.12) compared with tamoxifen (18).

Several trials have also investigated the role of endocrine therapy in combination with other targeted therapies. For example, in the randomized phase II UNICANCER-NEOPAL study, the combination of neoadjuvant palbociclib and letrozole resulted in slightly lower pCR rates compared with neoadjuvant third-generation chemotherapy, but the rates of clinical response and breast-conserving surgery were similar, with less frequent serious adverse events (19). Another study compared different doses of neoadjuvant fulvestrant (500 mg/month versus 250 mg/month) given for 16 weeks prior to surgery (20). Similar to what has been observed in the metastatic setting, the study demonstrated that the higher dose of fulvestrant was superior and had a greater antiproliferative effect. At week 16, tumor response rates were 22.9 and 20.6% for fulvestrant 500 and 250 mg, respectively, with considerable decline in all markers by both imaging and the ER/PR scoring method.

CONFIDENTIAL

This material is the property of the [UC Irvine Chao Family Comprehensive Cancer Center](#). Do not disclose or use except as authorized in writing by the study sponsor.

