10.1 Study Design

This study is a prospective, open-label, single-centered, phase II trial.

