Table X1 presents sample size of Simon's two-stage design. Where n is the total number of subjects, n₁ is the number of subjects accrued during stage 1, if r₁ or fewer responses are observed during stage 1, the trial is stopped early for futility. If r₂ or fewer responses are observed by the end of stage two, then no further investigation of the drug is warranted, EN₀ is the expected sample size for the trial when response rate is p₀ and p₀ and p₁ are the response probabilities under the null and under the alternative hypothesis. Thus, the null hypothesis that the true response rate is 10% will be tested against a one-sided alternative. In the first stage, 10 patients will be accrued. If there are one or fewer responses in these 10 patients, the study will be stopped. Otherwise, 19 additional patients will be accrued for 29. The null hypothesis will be rejected if 6 or more responses are observed in 29 patients. This design will yield a type I error rate of 0.0471 and power of 80% when the true response rate is 0.3. Thus, we anticipate recruiting 29 evaluable participants with at least 10 in stage 1. (Simon 1984, Jung et al 2004) (16, 17). Given the sample size of 30 participants, power in the statistical design will be low for the secondary and exploratory endpoints. Efficacy of the study as measured by estimating the objective response rate in the breast and/or the axillary lymph nodes or determining if the combination of Abemaciclib and Fulvestrant increases the percentage of patients who undergo breast conserving surgery will be measured by constructing 95% CI. We plan to use survival analysis methods such as Kaplan- Meier estimates of survival probability for univariate analysis and log rank tests in order to test for differences among different patient characteristics such as age group for recurrence or disease-free survival. For multivariate analysis in order to examine survival adjusted for a number of covariates we plan to use the Cox proportional hazards model. In order to examine the safety and toxicity which will be determined by the incidence of treatment-emergent, treatment-related adverse events (TRAEs), and serious adverse events (SAE) we plan to monitor side effects and adherence to the protocol throughout the duration of the study. Interim analyses will be performed to assess the presence of side effects. Contingency tables will be constructed to compare the proportion of patients with side effects by study characteristics as age, race ethnicity and other clinical and epidemiologic characteristics. Distributions of all data items will be generated and examined for the presence of outliers, in order to assess the general form of the distributions, and to compute measures of central tendency and variability. Trellis graphics will be used for data display including histograms, boxplots, and Q-Q normal plots. In addition, we plan to examine if genomic analysis of patient matched breast tissue samples and serial mutational tracking of circulating tumor DNA can identify new mechanisms of endocrine resistance and how

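### The primary endpoint, pCR, has conflicting definitions in Sections 2.4, 6.1 and 10.0, and the protocol does not say which one governs

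*Combined protocol and SAP*

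**What the plan says.** Three sections define the primary endpoint.

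- Section 2.4 (Endpoints): "pathological complete response (pCR) as defined by no evidence of tumor cells in the final surgical specimen".
- Section 6.1 (Pathologic Complete Response): "No histologic evidence of microscopic invasive tumor at the primary tumor site in the surgical specimen (ypT0 or ypTis".
- Section 10.0 (Statistical Considerations): "A complete pCR is defined as the absence of invasive cancer in the tumor and/or the axillary lymph node in the surgical pathology specimen".

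The primary objective (synopsis and Section 2.1) names pCR without defining it. Section 10.2 sets the decision rule in terms of responses: "the null hypothesis that the true response rate is 10% will be tested against a one-sided alternative". At stage 1, "If there are one or fewer responses in these 10 patients, the study will be stopped". At the end, "The null hypothesis will be rejected if 6 or more responses are observed in 29 patients". Section 10.2 does not say what a response is. The synopsis paragraph on statistical methodology measures efficacy by the objective response rate or by breast-conserving surgery, and does not mention pCR. The only pCR benchmark is in Section 10.0, "only 2 to 10 percent of patients with ER + disease achieve a pCR with NACT", and no definition is attached to it.

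**The concern.** The sections do not classify patients in the same way. A patient with only in situ carcinoma left passes 6.1 and, read literally, fails 2.4. A patient with a clear breast specimen and a positive node passes 6.1, and passes or fails 10.0 depending on how the and/or is read. Section 3.1.2 admits Stage I to III disease, so residual nodal disease can occur.

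The Simon cut-offs are small counts (1 versus 2 of 10, 5 versus 6 of 29), so one patient scored differently can stop the trial or reverse its conclusion. Section 10.1 says "This study is a prospective, open-label, single-centered, phase II trial", and there is one treatment arm. With no governing definition, the choice could be made after the pathology results are known.

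It is also unclear under which definition the 10% null and the 30% alternative are pCR rates.

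**Working it through.** **Step 1. Compare the definitions.**

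| Residual disease at surgery | 2.4 | 6.1 | 10.0 |
|---|---|---|---|
| None | pCR | pCR | pCR |
| In situ only, nodes clear | not pCR (literal reading) | pCR | pCR |
| Breast clear, node positive | depends on whether the specimen includes nodes | pCR | not pCR under 'and'; pCR under 'or' |
| Invasive in breast, nodes clear | not pCR | not pCR | not pCR under 'and'; pCR under 'or' |

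On in situ disease, 2.4 is the outlier. On nodes, 6.1 is silent and 10.0 is undetermined.

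**Step 2. Reproduce the plan's own figures.** Inputs from Section 10.2 and Table x1: n1 = 10, r1 = 1, N = 29, r2 = 5, p0 = 0.10, p1 = 0.30.

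- Early stopping at p0: 0.9^10 + 10 × 0.1 × 0.9^9 = 0.3487 + 0.3874 = 0.7361.
- Expected N at p0: 10 + 19 × (1 − 0.7361) = 15.0.
- Probability of rejecting the null: G(p) = Σ over x = 2 to 10 of P(X1 = x) × P(X2 ≥ 6 − x), with X1 ~ Bin(10, p) and X2 ~ Bin(19, p).
- G(0.10) = 0.0471 and G(0.30) = 0.8051.

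All four match Table x1.

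**Step 3. One patient at a boundary.** This step and the next treat a response as a pCR.

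- Final analysis: 6 of 29 are ypT0 or ypTis, and one of the six has only in situ disease. Under 6.1 the count is 6 and the null is rejected. Under 2.4 it is 5 and the null is not rejected.
- Stage 1: 2 of 10 are ypT0 or ypTis, and one of the two has only in situ disease. The trial continues under 6.1 and stops under 2.4.

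**Step 4. How often the conclusion would differ (illustration).** Let b be the true pCR rate under 6.1 and d the share of those pCRs with only in situ disease left. The documents give no value for d; 5%, 10% and 20% are assumed here. Every 2.4 pCR is also a 6.1 pCR, so the two conclusions differ with probability G(b) − G(b(1 − d)).

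| d | b = 0.30 | b = 0.10 |
|---|---|---|
| 5% | 0.8051 − G(0.285) = 0.8051 − 0.7655 ≈ 0.040 | 0.0471 − G(0.095) = 0.0471 − 0.0382 = 0.009 |
| 10% | 0.8051 − G(0.27) = 0.8051 − 0.7199 = 0.085 | 0.0471 − G(0.09) = 0.0471 − 0.0305 = 0.017 |
| 20% | 0.8051 − G(0.24) = 0.8051 − 0.6099 = 0.195 | 0.0471 − G(0.08) = 0.0471 − 0.0183 = 0.029 |

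This covers only the nested pair 2.4 and 6.1 on in situ disease. Disagreement over nodes is not modelled; the 'or' reading of 10.0 is not nested in 6.1.

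**The case against.** The best defence is that 6.1 plainly governs. It is the measurement section, it alone uses staging codes, and it names the site. Section 10.0 supports it on invasive disease, and its and/or sentence opens a literature narrative rather than an analysis rule. On this view, 2.4 is loose shorthand and two summary sentences need tidying. That is a natural reading, and it narrows the conflict. It does not remove it: 2.4 is the passage that states what the primary endpoint is, and no text gives 6.1 precedence.

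A second objection is that the documents never say that pCR drives the Simon rule. That is correct. Section 10.2 leaves responses undefined and the synopsis measures efficacy by ORR. The link is inferred from pCR being the primary endpoint, and the boundary example depends on it. The same gap is also a reason to define the term.

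A third is that the size rests on an assumed rate. That stands as well: nothing in the documents favours 20% over 5%.

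A reader might go further and infer any of the following, which the documents do not support.

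- *The design arithmetic is wrong.* It reproduces exactly.
- *A breast-only pCR is improper.* It is a permissible choice; the fault is that no choice is stated.
- *The sample size must rise.* That depends on how the rates are restated. A search for the optimal Simon design (one-sided alpha at most 0.05, power at least 0.80) gives N = 31 for 0.09/0.27, but 24 for 0.09/0.30 and 26 for 0.111/0.333.
- *The definition will be picked to suit the data.* The text leaves room for that and gives no sign that it is intended.

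**Conclusion.** The point holds as an internal inconsistency: the primary endpoint is wrong as written, not merely short of detail. Sections 2.4 and 6.1 score a patient with residual in situ disease in opposite ways, and 10.0 leaves nodes undecided. The conflict itself needs no assumption.

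Its consequence rests on the inference that a Simon response is a pCR. Given that, one patient can reverse either decision. How often this would happen cannot be known from the documents; the figures in Step 4, about 4% to 20% of trials at a 6.1 rate of 30% and about 1% to 3% at 10%, are an illustration under assumed discordance of 5% to 20%. Alpha 0.0471 and power 0.8051 stand for p0 = 0.10 and p1 = 0.30, whichever definition those rates belong to.

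**What to change.** Before any surgical pathology is scored for the endpoint:

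1. Choose one pCR definition and use it word for word in Sections 2.4, 6.1 and 10.0. It should state whether in situ disease is allowed and whether nodes count, and replace the and/or. If nodes count, add a scoring rule for patients with no nodes sampled. No section requires nodal sampling, although the PEPI score (Section 2.2.6, Appendix E) already needs nodal stage.
2. State in Section 10.2 that a response in the Simon rule is this pCR.
3. Align the synopsis statistical paragraph so that pCR is the primary efficacy measure and ORR is secondary.
4. Confirm that 0.10 and 0.30 are rates under the chosen definition. If they are not, restate alpha and power.
5. Report the other definitions as a sensitivity analysis.

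The cost is a short amendment and one extra tabulation. The reported pCR count may be lower or higher than under another wording. If the rates have to be restated, the design figures may move in either direction.

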The standard of care options for Post-menopausal patient who develop localized or locally advanced recurrent HR+ Breast cancer while on adjuvant endocrine therapy remains to be surgical resection. The treatment depends on the type of local treatment they received at the initial diagnosis. Recurrence can happen after a lumpectomy and radiation or following mastectomy. Mastectomy is the surgical standard of care for most patients with a local recurrence following breast conserving surgery and radiation. Surgery in the form of wide local excision is recommended for post mastectomy chest wall recurrence. The role of radiation in the management of localized recurrence also depends upon if patients received adjuvant radiation at the initial diagnosis. Surgery and radiation in recurrent HR + breast cancer only address local control. Patients with recurrent breast cancer are at risk of developing metastatic breast cancer, have microscopic metastasis and many have evidence of endocrine resistance. Furthermore, extensive loco-regional recurrence is not amenable to surgical resection alone. Surgery and radiation does not address endocrine resistance nor does it treat microscopic metastasis. Hence, addressing endocrine resistance as well as adopting a targeted Neo-Adjuvant approach based on patient's tumor profiling and then treating them with the Abemaciclib and Fulvestrant to downstage the tumor, limit chemotherapy induced toxicity is the next logical step in the management of patients. These patients often land up getting Neo-Adjuvant chemotherapy. Few achieve a complete pathologic response and many are subjected to severe peri-operative complications. Hence, there continues to be an unmet medical need to develop alternate therapies that are less toxic and provide better outcomes. Neoadjuvant endocrine therapy can be an alternative option to chemotherapy in Hormone Receptor positive (HR+) tumors, particularly for postmenopausal women. Unlike in premenopausal women, available data suggest that NET is associated with similar response rates and rates of breast- conserving surgery (BCS) as NACT with lower toxicity, although survival data with NET are not yet available (11-15).

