2.2 Secondary Objectives

- 2.2.1 To determine the objective response rate (ORR) in the breast and/or the axillary lymph nodes
- 2.2.2 To determine if the combination of Abemaciclib and Fulvestrant increases the percentage of patients who undergo breast conserving surgery
- 2.2.3 Recurrence disease-free survival
- 2.2.4 Safety and Toxicity
- 2.2.5 To determine the percentage change in the Ki 67 from baseline to the treated specimen after breast surgery
- 2.2.6 To determine the preoperative endocrine prognostic index (PEPI) score as predictors of response to Neo-adjuvant Abemaciclib and Fulvestrant

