3.1 Inclusion Criteria

- 3.1.1 Patients must have a diagnosis of HR+ breast cancer. To fulfill the requirement of HR+ disease, a breast cancer must express, by immunohistochemistry (IHC), at least one of the hormone receptors (ER, progesterone receptor [PgR]) as defined in the relevant American Society of Clinical Oncology (ASCO)/College of American Pathologists (CAP) Guidelines (Hammond et al. 2010):
 - For ER and PgR assays to be considered positive, $\geq 1\%$ of tumor cell nuclei must be immunoreactive by immunohistochemistry (IHC) (Hammond et al. 2010).
- 3.1.2 Patients must have Loco regional breast cancer (Stage I, Stage II and stage III per AJCC 8th edition criteria for staging of breast cancer)
- 3.1.3 Patients must have localized recurrence while on adjuvant endocrine therapy
- 3.1.4 Patients must have any known molecular evidence of endocrine resistance by next generation sequencing
- 3.1.5 Age ≥ 18 years.
- 3.1.6 ECOG performance status 0-1
- 3.1.7 Have post-menopausal status as defined by following:
 - Prior bilateral oophorectomy
 - Age ≥ 60 years
 - Age < 60 and amenorrheic (non-treatment-induced amenorrhea secondary to tamoxifen, toremifene, ovarian suppression, or chemotherapy) for at least 12 months. Follicle-stimulating hormone (FSH) and estradiol must be in the postmenopausal range.
- 3.1.8 Have at least one measurable disease as defined per RECIST 1.1
- 3.1.9 Adequate organ and marrow function as defined below:
 - Hemoglobin* > 8 g/dL
 - Absolute neutrophil count $\geq 1,500/\text{mcL}$
 - Platelets $\geq 100,000/\text{mcL}$
 - Total bilirubin $\leq 1.5 \times$ institutional ULN

Patients with Gilbert's syndrome with a total bilirubin ≤ 2.0 times ULN and direct bilirubin within normal limits are permitted

 - AST (SGOT)/ALT (SPGT) $\leq 2.5 \times$ institutional ULN
 - Creatinine $\leq 1.5 \times$ institutional ULN

**Patients may receive transfusion of packed red blood cells (PRBC) to achieve this hemoglobin level at the discretion of the investigator; however, initial study drug treatment must not begin earlier than the day after the PRBC transfusion.*

CONFIDENTIAL

This material is the property of the [UC Irvine Chao Family Comprehensive Cancer Center](#). Do not disclose or use except as authorized in writing by the study sponsor.

- 3.1.10 Able to swallow oral medications

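### Section 6.1 judges pCR only at the primary tumor site, which is undefined for recurrent disease, so a node-only recurrence could be scored a pCR despite viable tumor; 2.4 and 10.0 define pCR differently and no section says which applies

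*Combined protocol and SAP*

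**What the plan says.** The combined protocol and SAP defines the primary endpoint in three places.

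- Section 2.4 (Endpoints): "The primary endpoint is pathological complete response (pCR) as defined by no evidence of tumor cells in the final surgical specimen". It sets no site limit.
- Section 6.1 (Pathologic Complete Response): "No histologic evidence of microscopic invasive tumor at the primary tumor site in the surgical specimen (ypT0 or ypTis". It covers one site, accepts residual in situ disease, and has no ypN term.
- Section 10.0 (Statistical Considerations): "absence of invasive cancer in the tumor and/or the axillary lymph node in the surgical pathology specimen".

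On the population, 3.1.3 states "Patients must have localized recurrence while on adjuvant endocrine therapy" and 3.1.2 states "Patients must have Loco regional breast cancer", Stage I to III. No criterion requires that the recurrence lie in the breast. Section 1.4 discusses recurrence after lumpectomy and after mastectomy, including "Surgery in the form of wide local excision is recommended for post mastectomy chest wall recurrence". The first secondary objective (2.2.1) is "To determine the objective response rate (ORR) in the breast and/or the axillary lymph nodes".

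On the decision rule, 10.2 states that "the null hypothesis that the true response rate is 10% will be tested against a one-sided alternative". It stops after 10 patients if there are one or fewer responses, and rejects the null with 6 or more responses in 29. It speaks of responses throughout and does not point to any of the three definitions.

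**The concern.** The wording of 6.1 suits a newly diagnosed breast tumor, where the primary site is where the disease is. In this trial the original tumor has already been treated, and the disease under treatment is a recurrence. The protocol never says whether the primary tumor site means the original site or the site of the current lesion.

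The clearest problem case is an axillary-only recurrence. The breast site has no invasive tumor at entry and none at surgery, so the patient is ypT0 whatever happened in the nodes. The same holds for an in-breast recurrence away from the original site, if primary site means the original one. Such a patient would be a success under 6.1 that carries no information about the drugs.

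The trial has a single arm and low thresholds (2 of 10 to continue, 6 of 29 to succeed), so a few such patients can alter the conclusion.

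**Working it through.** **1. The definitions applied to one patient.** Take an axillary-only recurrence with viable nodal cancer in the surgical specimen and no tumor in the breast.

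| Section | Scored as pCR? | Reason |
|---|---|---|
| 2.4 | No | Tumor cells are present in the specimen |
| 6.1 | Yes, as written | No invasive tumor at the primary site; nodes not considered |
| 10.0 | Unclear | The and/or can be read either way when only the nodes are involved |

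**2. The plan's own figures.** Inputs from 10.2: n1 = 10, r1 = 1, N = 29, r2 = 5, p0 = 0.10, p1 = 0.30. With X1 ~ Bin(10, p) and X2 ~ Bin(19, p),

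P(success) = Σ over x = 2..10 of P(X1 = x) × P(X2 ≥ 6 − x).

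This gives 0.0471 at p = 0.10 and 0.8051 at p = 0.30. The probability of early stopping under the null is 0.7361. All three match the plan's table.

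**3. Adding patients who count as pCR regardless of drug.** Suppose 6.1 governs and k of the 29 are such patients, placed at random across the stages. The number s falling in stage 1 is hypergeometric, with weight C(10, s) × C(19, k − s) / C(29, k). The remaining 10 − s and 19 − (k − s) patients respond independently with probability p. Stage 1 passes if s plus its other responses is at least 2; success needs k plus all other responses to be at least 6.

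Worked case, k = 1 and p = 0.10:

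- in stage 2 (weight 19/29 = 0.6552): success chance 0.0942
- in stage 1 (weight 10/29 = 0.3448): success chance 0.1285
- total: 0.6552 × 0.0942 + 0.3448 × 0.1285 = 0.106

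| True pCR rate in the others | k = 0 | k = 1 | k = 2 | k = 3 |
|---|---|---|---|---|
| 10% (the null) | 0.047 | 0.106 | 0.213 | 0.377 |
| 5% | 0.002 | 0.008 | 0.032 | 0.101 |
| 2% | <0.001 | 0.0002 | 0.0014 | 0.0105 |
| 0% | 0 | 0 | 0 | 0 |

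Both k and the rate in the others are assumptions. Section 10.0 gives 2 to 10 percent as the pCR range with neoadjuvant chemotherapy in ER-positive disease, so the 10% row sits at the top of that range.

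**4. The same point as a share of patients.** If each patient has probability f of being such a case, the scored rate is f + (1 − f)p. At p = 0.10 and f = 5%, 10%, 20% the scored rates are 0.145, 0.190 and 0.280, and the success chances are 0.181, 0.384 and 0.751. At p = 0 they are 0.002, 0.047 and 0.431. A share of 20% means about 0.20 × 29 = 5.8 patients. The documents give no value for f.

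**The case against.** The strongest reply is that 2.4, the Endpoints section, already excludes the problem case: viable tumor in the excised nodes or chest wall is tumor in the specimen. That is right, and it limits the point to an unresolved conflict between definitions. It does not remove it. No section gives 2.4 precedence over 6.1, which is the measurement section, and 2.4 does not require the specimen to include each site of disease.

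The primary tumor site could also mean the site of the current lesion, since 3.1.2 stages the enrolled disease as I to III. An in-breast recurrence is then judged properly. That reading is nowhere stated, and it leaves no rule for node-only disease.

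Node-only enrolment is itself an inference. The protocol speaks of local or localized recurrence, and breast MRI is the scheduled response imaging (5.1.13 and 5.5), which suggests mainly in-breast disease. This stands as a reason to expect few such patients. It does not exclude them.

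A reader might infer three stronger claims that the documents do not support:

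- **Such patients meet the primary endpoint before any drug is given.** pCR needs a surgical specimen after therapy, and under 2.4 they do not meet it at all.
- **A chest-wall recurrence is automatically a pCR.** After mastectomy the chest wall may be read as the tumor bed, and the excised lesion is itself the specimen.
- **The trial can succeed with no drug effect.** With 1 to 3 such patients and no pCR in the rest, success is impossible, because six are needed. It becomes likely only at shares for which the documents give no basis.

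**Conclusion.** The point holds as a definitional defect in the sole primary endpoint. Section 6.1 ties pCR to a site that is undefined for a recurrence and omits the nodes. It disagrees with 2.4 and possibly with 10.0 on the same patient, and the two-stage rule does not say which definition it counts.

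The size is conditional. It requires that 6.1 governs, that at least one patient has disease only away from the primary site, and that the other patients' pCR rate is near the 10% null. Then one such patient more than doubles the one-sided error, from 0.047 to 0.106, and two or three take it to 0.213 or 0.377. If the others' rate is 5%, it takes three such patients to exceed the planned error (0.101). These figures show sensitivity and do not estimate the trial's actual error rate. If pCR is tied to all sites of recurrent disease, the stated 0.0471 and 0.8051 stand.

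**What to change.** Use one pCR definition, worded identically in 2.4, 6.1 and 10.0: no residual invasive tumor in the surgical specimen at any site of recurrent disease documented at baseline (breast, chest wall and/or regional nodes). State once whether residual in situ disease is compatible with pCR, since 2.4 and 6.1 now differ on it. In 10.2, say that this definition supplies the counts at both Simon stages, and that a patient counts as a pCR only when every baseline disease site was pathologically assessed. Take the baseline sites from the target and non-target lesion record that 6.2.2 already requires. Amending 6.1 alone would leave the three sections in conflict.

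The cost is a short text amendment. The observed pCR rate may be slightly lower, and patients without pathology for a baseline site count as non-responders. The rule governs scoring only and prescribes nothing about the extent of surgery. Sample size and thresholds are unchanged.
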